#### **6.10.1.4 General Considerations**

Due to the small sample size ( $n = 18$ ) which was not based on formal power considerations with respect to statistical hypothesis testing, no formal hypothesis testing will be employed. Although p-values may be calculated they should be interpreted as exploratory rather than confirmatory given the small sample size, lack of multiplicity adjustment, and exploratory nature of the hypotheses they may be testing.

Instead, descriptive statistical techniques will be used to identify differences between the doses of moxidectin with the objective of describing an exposure-response association between the dose groups and parasitological outcomes, and/or observing a single dose that appears to have the 'best' parasitological effect while maintaining an acceptable safety profile.

All RCM assessment data will be listed, including the derived flag for mites considered dead at each time point and time to death of mite.

#### **6.10.1.5 Summaries**

##### **Mortality rate for adult scabies mites**

The summary of mortality rate data will include the number and percentage of dead adult scabies mites, presented by dose group for each post-Baseline RCM time point.

The total number of live adult scabies mites identified at Baseline (and used as the denominator for the percentages), will also be indicated in the summary. Clopper-Pearson 95% CIs will be presented for all percentages where independence among mites within subjects is assumed.

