## 15 STATISTICAL ANALYSIS

### 15.1 Statistical Methods

The study is a randomized, double-blind, proof-of-concept trial designed to describe the association between single moxidectin doses and various parasitological outcomes observed over a 28-day follow-up period. Subjects will continue to be followed for safety to Week 12. Following Screening, eligible consenting subjects will be randomized to one of the 3 initial moxidectin dose groups, 2, 8, or 20 mg. The randomization will be stratified by site and within each site subjects will be randomized using a 1:1:1 allocation ratio. After review of the accumulating data by the Protocol Steering Committee, the randomization scheme may be modified to accommodate the addition or deletion of doses such that the final target sample size of 6 subjects per dose retained/added after the unblinded data review is accommodated. The primary objective of this proof-of-concept study is to identify an optimal dose of moxidectin for further study.

The target sample size,  $n = 6$  per completed dose group, was selected to be practical and an adequate sample size for full characterization of pharmacokinetic profile across the dose ranges studied. Sample size was not based on formal power considerations with respect to statistical hypothesis testing, and as such, the focus of the statistical analysis will be descriptive and exploratory. Nonetheless, statistical models for estimation and hypothesis testing to assess various parasitological assessments with respect to dose may be conducted. It is recognized that the sample size may not adequately support more complex models. When this is the case it will be noted. Given the exploratory nature of the study, no adjustment for multiple comparisons or Protocol Steering Committee data reviews will be made. Given the small sample size per dose group, descriptive analyses per site may be difficult to interpret.

For most analyses, the unit of analysis will be the subject; however, some analyses may be conducted where the unit of analysis may be the individual scabies mite. When this is the case, the unit of analysis will be clearly identified. Analyses using the individual scabies mite as the unit of analysis will address the potential lack of independence between mites belonging to the same subject.

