## 15.7 General Analytic Methods

### 15.7.1 Overview

The focus of the statistical analysis will be descriptive and exploratory. Statistical models for estimation and/or hypothesis testing to assess various parasitological assessments with respect to dose may be conducted; however, it is recognized that the sample size may not adequately support more complex models that may be utilized to account for the clustering of scabies mites within subjects. When this is the case it will be noted. Given the exploratory nature of the study, no adjustment for multiple comparisons will be made.

Detailed methods will be provided in the SAP.

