**CONFIDENTIAL**

(proportion) of subjects within each category. Where feasible, 95% confidence intervals will also be provided. Summary measures where the mite is the unit of analysis will be identified. Due to the possible lack of independence between scabies mites observed within the same subject, where possible, “robust” standard errors and/or estimates resulting from models accounting for the clustering will be presented along with any unadjusted estimates.

For the key efficacy endpoints, the PPAS will be used as the primary analysis set. If the FAS differs from the PPAS, sensitivity analyses using the FAS may also be conducted to assess differences between the two analysis sets.

For continuous subject level endpoints such as the average proportion of dead adult scabies mites per subject, pairwise comparisons between dose groups may be conducted using an unpaired t-test or nonparametric Wilcoxon Rank-Sum Test if the assumptions of the t-test do not appear to hold.

Binary endpoints at the subject level such as clinical cure rates may be examined via logistic regression models or chi-square tests with estimates of the relative risk and their associated 95% confidence intervals. Where appropriate exact methods will be employed.

Point estimates and confidence intervals for the mortality rates when the scabies mite is the unit of analysis will be estimated using a logistic regression model with “robust” standard errors. Additionally, the analysis of these data using a Generalized Linear Mixed Models (GLMMs) with random intercepts or a Generalized Estimating Equation (GEE) model may be employed. The time-to-death for an individual scabies mite may be analyzed using a frailty survival model.

Because of the small sample sizes, it is recognized that convergence or estimation issues may arise for some of more complex exploratory models that may be conducted.

Further details will be provided in the SAP.

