#### **6.10.1.2 Primary Endpoints**

Four separate endpoints will be analyzed in order to assess death of adult scabies mites, all of which will be considered key primary efficacy endpoints. Analysis of the death of adult scabies mites will be performed using the individual scabies mite as the unit of analysis and also the subject as the unit of analysis.

The endpoints to be analyzed using the scabies mite as the unit of analysis will be:

- Mortality rate for adult scabies mites at each post-Baseline RCM time point. Mortality rate at each time point will be calculated as the proportion of the total number of dead adult scabies mites from among the total number of live adult scabies mites identified at Baseline.
- Time to death of adult scabies mites for those identified as live at Baseline. Time to death of each adult scabies mite will be calculated in hours as (Date and time of first RCM assessment where mite confirmed dead) – (Date and time of study drug administration), for mites with confirmed death during the study. For mites without confirmed death during the study, time to death will be calculated in hours as (Date and time of Day 28 RCM assessment) – (Date and time of study drug administration), i.e. worst case.

The endpoints to be analyzed using subject as the unit of analysis will be:

- Mean proportion of dead adult scabies mites per subject at each post-Baseline RCM time point. The proportion of dead adult scabies mites for each individual subject at each time point will be calculated as the number of dead adult scabies mites from among the live adult scabies mites identified at Baseline for that subject.

- Proportion of subjects with 100% dead adult scabies mites from among the live adult scabies mites identified at Baseline for that subject, at each post-Baseline RCM time point.

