#### **Time to death of adult scabies mites**

Time-to-death of adult scabies mites (hours) for each mite identified as live at Baseline is defined as:

*(Date and time of first RCM assessment where mite confirmed dead) – (Date and time of study drug administration).*

The time-to-death of adult scabies mites will be interval censored. For those mites with confirmed death during the study, the beginning of the interval will be the administration of study drug and the end of the interval will be the first RCM assessment where the mite is confirmed dead. For mites without confirmed death during the study, or still alive prior to or on the start date of any rescue medication exposure, the time-to-death will be right censored where the beginning of the interval will be the administration of study drug and the end of the interval will be the Day 28 RCM assessment (i.e. worst case), calculated in hours as:

*(Date and time of Day 28 RCM assessment) – (Date and time of study drug administration).*

Descriptive statistics will be presented for the time-to-death of adult scabies mites by dose group. This will include a summary excluding mites without confirmed death during the study (or still alive prior to or on the start date of any rescue medication exposure), as well as a separate summary including mites without confirmed death during the study or still alive prior to or on the start date of any rescue medication exposure, with the time to death censored as described above. A separate summary will present for each dose group, the number of mites identified as alive at Baseline, and the number and percentage of dead mites at the end of the study along with the Clopper-Pearson 95% CI for the percentage where independence among mites within subjects is assumed. The number and percentage of mites that are censored will also be summarized, along with Kaplan Meier (KM) estimates for the 25th, 50th and 75th percentiles of time to mite death and corresponding 95% CIs. The time-to-death of adult scabies mites will also be presented graphically using a KM plot.

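### The mite mortality rate gets only intervals that assume independent mites within a subject, which departs from the protocol without being recorded; they are too narrow if clustering is moderate or strong

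*SAP*

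**What the plan says.** Protocol 15.1 gives a general undertaking: "Analyses using the individual scabies mite as the unit of analysis will address the potential lack of independence between mites belonging to the same subject". Protocol 15.7.3 makes it specific: "Point estimates and confidence intervals for the mortality rates when the scabies mite is the unit of analysis will be estimated using a logistic regression". The fit is to use a robust variance. Mixed models, GEE and frailty models are only optional there. The same section adds, as far as feasible and again meaning the robust kind: "standard errors and/or estimates resulting from models accounting for the clustering will be presented along with any unadjusted estimates". Protocol 15.7.1 warns that "the sample size may not adequately support more complex models that may be utilized to account for the clustering of scabies mites within subjects", and that this will be noted when it happens.

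SAP 6.10.1.5, on the mortality rate at each time point, states: "Clopper-Pearson 95% CIs will be presented for all percentages where independence among mites within subjects is assumed". For end-of-study deaths, in the time-to-death summary, it gives the percentage dead "along with the Clopper-Pearson 95% CI for the percentage where independence among mites within subjects is assumed". The SAP names no cluster-aware method for the mite-level rate. Section 6.10.1.7 allows post-hoc analyses under an addendum but specifies none.

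SAP 6.15 lists changes from the protocol: the full analysis set definition, imputation for the primary endpoint, and where eggs and scybala are summarised. The interval method is not among them.

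**The concern.** Each subject contributes 2 to 4 mites (SAP 6.10.1.1). They live on one host, so their outcomes may well be correlated. If they are, 18 mites on 6 subjects carry less information than 18 independent mites, and an interval that counts every mite as independent can be too short.

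Mite mortality is one of four endpoints, "all of which will be considered key primary efficacy endpoints" (SAP 6.10.1.2). SAP 6.10.1.4 says that "descriptive statistical techniques will be used to identify differences between the doses of moxidectin", in place of formal testing. Readers will therefore judge precision from the printed intervals. At stake is an overstatement of what about 6 subjects per dose can show about the mortality rate, together with a departure from a protocol commitment that a later reader could not trace.

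**Working it through.** **Text.** Set side by side, the documents give:

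| Item | Protocol | SAP |
|---|---|---|
| Interval for mite mortality | Logistic model, robust standard errors (15.7.3, firm) | Clopper-Pearson, independent mites (6.10.1.5) |
| Clustered beside unadjusted results | Yes, where possible (15.7.3) | Unadjusted only |
| Departure recorded | Failure of complex models to be noted (15.1, 15.7.1) | No entry in 6.15 |

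**Inputs.** About 6 subjects per dose group (SAP 3); 2 to 4 mites per subject (SAP 6.10.1.1); 95% level. The plan states no interval width, coverage or ICC for this endpoint, so there is no figure of its own to reproduce. The ICC is an assumption and is shown as a range.

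**Loss of information.** Design effect = 1 + (m − 1) × ICC for m mites per subject; effective number of mites = 6m / design effect. At ICC 0.4 and m = 3: 1 + 2 × 0.4 = 1.8, and 18 / 1.8 = 10 effective mites rather than 18.

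**Coverage.** Deaths within a subject are taken as beta-binomial with the stated ICC. Coverage of the independence-based interval was computed exactly and averaged over 27 equally spaced true rates from 30% to 95%. The 2–4 column gives each subject 2, 3 or 4 mites with equal chance.

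| ICC | 2–4 mites, mean % | 2 each, mean % | 4 each, mean % | 2–4 mites, true rate 50% | 2–4 mites, true rate 90% |
|---|---|---|---|---|---|
| 0 | 97.5 | 97.9 | 97.1 | 96.9 | 98.7 |
| 0.1 | 95.8 | 97.3 | 94.5 | 94.9 | 97.7 |
| 0.2 | 93.9 | 96.5 | 91.6 | 92.6 | 96.7 |
| 0.4 | 89.9 | 95.0 | 85.8 | 87.9 | 94.8 |
| 0.6 | 85.9 | 93.2 | 80.4 | 83.4 | 93.1 |
| 0.8 | 82.1 | 91.5 | 75.7 | 79.3 | 91.7 |

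With independent mites Clopper-Pearson covers more than 95%, and that margin absorbs weak clustering. With 2 mites each it lasts, on average, to an ICC of about 0.4. With 4 each it is used up near 0.1.

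**Interval with n = number of subjects.** With k subjects and observed proportion p, set x = kp (not rounded). Lower limit = 2.5% quantile of Beta(x, k − x + 1); upper limit = 97.5% quantile of Beta(x + 1, k − x). The lower limit is 0 at 0% dead and the upper limit is 1 at 100% dead.

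- 16 of 24 dead, 6 subjects: x = 6 × 16/24 = 4. Unadjusted 44.7% to 84.4%; companion 22.3% to 95.7%.
- 15 of 18 dead, 6 subjects: x = 5. Unadjusted 58.6% to 96.4%; companion 35.9% to 99.6%.
- 18 of 18 dead, 6 subjects: lower limits 0.025^(1/18) = 81.5% and 0.025^(1/6) = 54.1%.

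For 2–4 mites and ICC 0 to 0.8, the companion's mean coverage is 99.2% to 100% and its mean width is 0.67 to 0.69, against 0.40 to 0.42 for the unadjusted interval.

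**The case against.** The strongest reply has four parts.

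1. *The assumption is disclosed and the study is descriptive.* Both stand. The SAP states independence at both places and plans no formal testing. Stating the assumption does not, however, tell a reader that the protocol's method was dropped, or why.

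2. *The protocol foresaw that clustering models might fail.* This stands as a reason not to fit them. With about 6 clusters per dose, robust standard errors tend to be too small, and the logistic estimate is not finite at 0% or 100% dead. But the caveat concerns more complex models and says failure will be noted. It does not waive the promised interval without a record.

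3. *The subject is already a unit of analysis.* This stands and narrows the point. SAP 6.10.1.5 summarises the proportion dead per subject, with a mean and SD (SAP 6.1), and gives an exact interval for the proportion of subjects with all mites dead. A reader might infer that the SAP makes no allowance for clustering anywhere; these rows show otherwise. At 18/18 dead, the subject-level row already reports 54.1% to 100%. But the first of these rows lists no interval, and the second estimates a different quantity.

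4. *Weak clustering does no harm.* This stands. A reader might infer that any clustering makes these intervals too narrow. The table shows no average shortfall at ICC 0.1, nor with 2 mites each up to about 0.4.

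Two other tempting readings also fail. The shared dose is no source of correlation here, because each interval is computed within one dose group. Nor do the documents support saying that the dose choice or the steering committee's review is compromised. SAP 5.1 names mite mortality as a guide for the committee, but does not say these intervals are supplied to it, and no decision rule uses them.

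**Conclusion.** The point holds in a limited form. The departure from the protocol is certain from the text: a firm commitment on the interval for a key primary endpoint was replaced, and SAP 6.15 does not say so. What is missing is a cluster-aware interval for the mite mortality rate itself.

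The size of the effect is conditional. Under the beta-binomial assumption with 6 subjects and 2 to 4 mites each, mean coverage falls from about 96% at ICC 0.1 to 90% at 0.4 and 82% at 0.8. The shortfall is larger at mid-range mortality than near 90%, and larger with 3 or 4 mites per subject than with 2. The true ICC is unknown, so the documents support saying that the intervals are too narrow under moderate or strong clustering, not that they are too narrow in this trial.

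**What to change.** In SAP 6.10.1.5, for both the mortality rate at each time point and the end-of-study percentage:

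- Keep the present interval, labelled *unadjusted, assumes independent mites*.
- Beside it, pre-specify one interval for the same rate that allows for clustering and can be computed at 0% and 100% dead. The Clopper-Pearson form with n equal to the number of subjects in the dose group, given above, is one example.
- Label that example *conservative outer bound, n = number of subjects*. A label such as *fully dependent mites (ICC = 1)* would be wrong: with 3 mites in each of 6 subjects, full dependence allows only multiples of 3 dead, so 16/18 or 17/18 would contradict it.

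In SAP 6.15, record that the protocol's logistic interval with robust standard errors is not used, and why: about 6 clusters per dose and no finite estimate at 0% or 100% dead.

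The cost is some SAP wording, one extra column and a few lines of code. The drawback is that the companion interval is wide, with mean coverage of about 99% to 100%. At 100% dead it also repeats the interval already reported for subjects with all mites dead. It should be read as an outer bound beside the unadjusted interval, not as a replacement.

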#### **Time to death of adult scabies mites**

Time-to-death of adult scabies mites (hours) for each mite identified as live at Baseline is defined as:

*(Date and time of first RCM assessment where mite confirmed dead) – (Date and time of study drug administration).*

The time-to-death of adult scabies mites will be interval censored. For those mites with confirmed death during the study, the beginning of the interval will be the administration of study drug and the end of the interval will be the first RCM assessment where the mite is confirmed dead. For mites without confirmed death during the study, or still alive prior to or on the start date of any rescue medication exposure, the time-to-death will be right censored where the beginning of the interval will be the administration of study drug and the end of the interval will be the Day 28 RCM assessment (i.e. worst case), calculated in hours as:

*(Date and time of Day 28 RCM assessment) – (Date and time of study drug administration).*

Descriptive statistics will be presented for the time-to-death of adult scabies mites by dose group. This will include a summary excluding mites without confirmed death during the study (or still alive prior to or on the start date of any rescue medication exposure), as well as a separate summary including mites without confirmed death during the study or still alive prior to or on the start date of any rescue medication exposure, with the time to death censored as described above. A separate summary will present for each dose group, the number of mites identified as alive at Baseline, and the number and percentage of dead mites at the end of the study along with the Clopper-Pearson 95% CI for the percentage where independence among mites within subjects is assumed. The number and percentage of mites that are censored will also be summarized, along with Kaplan Meier (KM) estimates for the 25th, 50th and 75th percentiles of time to mite death and corresponding 95% CIs. The time-to-death of adult scabies mites will also be presented graphically using a KM plot.

#### **Proportion of dead adult scabies mites per subject**

The proportion of dead adult scabies mites per subject (calculated from among the live adult scabies mites identified at Baseline for the subject) will be summarized via descriptive statistics including the mean proportion, presented by dose group for each post-Baseline RCM time point.

#### **Proportion of subjects with 100% dead adult scabies mites**

The number and percentage of subjects with 100% dead adult scabies mites from among the live adult scabies mites identified at Baseline for that subject will be presented, together with the Clopper-Pearson 95% CI for the percentage, by dose group for each post-Baseline RCM time point.

#### **6.10.1.6 Sensitivity Analysis**

Per [Section 6.4](#), the primary analyses may be repeated on the FAS post hoc if deemed worthwhile to assess any impact to the conclusions made.

Further sensitivity analyses, for example using different missing data or imputation approaches, may be considered post-hoc. This may include a completers analysis, repeating selected primary endpoint analyses without imputation of mite status due to missing data. Sensitivity analyses may also be added to assess the impact of imputations due to rescue medication or apparent new infections.

#### **6.10.1.7 Post-hoc Analysis**

Where deemed appropriate following review of the summaries described above, post-hoc analyses for one or more of the primary endpoints may be considered in order to further evaluate any differences between dose groups.

Any post-hoc analyses to be performed will be fully defined in a SAP Addendum prior to conducting the analyses, including details on the models to be applied, the hypotheses to be tested and the presentation of the results.

#### **6.10.2 Secondary Endpoints**

PK and PD are described in further detail in [Section 6.12](#) and [Section 6.13](#) of this SAP.

#### **6.10.3 Exploratory Endpoints**

All exploratory endpoints will be analyzed and summarized using the PPAS as the primary analysis set. Per [Section 6.4](#), selected exploratory endpoints may be repeated on the FAS post-hoc if deemed worthwhile to assess any impact to the conclusions made. Where this is the case, the following endpoints will be repeated:

- Presence and number of total mites and burrows assessed visually at Days 7, 14 and 28 (see [Section 6.10.3.1](#)).
- Changes in assessment of clinician-reported scabies symptomology (see [Section 6.10.3.2](#)).
- Clinical cure rate (see [Section 6.10.3.4](#)).

The exploratory endpoints will be assessed using descriptive summaries. However, if deemed of interest following review of the summaries, further analyses of these endpoints may be considered post-hoc.

With the exception of clinical cure rate, data are included in all exploratory endpoint summaries irrespective of any exposure to rescue medication. The impact of rescue medication on data used in the summaries for clinical cure rate are detailed further [Section 6.10.3.4](#).

